8.3.7 Toxicity

Toxicity will be assessed according to CTCAE 4.03 during RT, directly after RT and at 1, 3 and 6 months following RT [20]. If radiation myelopathy is suspected (i.e. deterioration according to the modified ASIA scale [19]), spinal MR-imaging will be performed.

9 Comparisons to Historical Control Group

The patients of this study who received high-precision RT with 5x5 Gy for MSCC will be matched to historical control group treated with 5x4 Gy of conventional RT between 2001 and 2016. This data set consists of 680 patients.

The patients of the control group are part of an already existing anonymized database. To be eligible for control group, patients fulfilling the same inclusion criteria and exclusion criteria as defined in the prospective phase II study are considered. Furthermore, to be consistent with efficacy analysis of phase II study, patients of the historical control group must have received at least 80% of the planned RT dose. This will lead to more than 600 patients qualifying for the comparison with the prospectively collected phase 2 data.

For comparison purposes, a propensity score approach will be applied to account for baseline differences between treatment arms to balance covariates and remove bias that may arise due to these confounders. A propensity score is a conditional probability of assignment to a particular treatment given a number of baseline covariates. Except for unmeasured potential confounding factors, patients having the same propensity score but assigned to different treatments will tend to have the same (or nearly the same) distributions on their background covariates and thus are considered to be similar to random assignment of treatments. To estimate the odds of receiving a specific radiotherapy a non-parsimonious multivariable logistic regression model will be estimated. Covariates to be included in the model will be the following ten prognostic factors [16]:

- Age (2 groups, depending on median age)
- Gender
- Type of primary tumor (breast cancer vs. prostate cancer vs. myeloma/lymphoma vs. lung cancer vs. other tumors)
- Interval from tumor diagnosis to MSCC (≤ 15 vs. > 15 months)
- Number of involved vertebrae (1-2 vs. ≥ 3)
- Other bone metastases at the time of RT (no vs. yes)
- Visceral metastases at the time of RT (no vs. yes)
- Time developing motor deficits prior to RT (1-7 days vs. 8-14 days vs. > 14 days)
- Ambulatory status prior to RT (no vs. yes)

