- Eastern Cooperative Oncology Group (ECOG) performance score (1-2 vs. 3-4)

Once estimated, adjustment will be accomplished by stratifying the data set on the propensity score, calculating the treatment effect within strata and then pooling the strata-specific treatment effect estimates.

Rosenbaum and Rubin have shown that perfect stratification based on the propensity score will produce strata where the average treatment effect within strata is an unbiased estimate of the true treatment effect [21]. Due to the differences in total sample size between the phase II study and the historical data set, the stratum boundaries will be based on the values of the propensity score for the phase II data alone.

One approach is to use quintiles of the estimated propensity scores to determine the cut-offs for the different strata. The success of propensity score approach will be examined by examining the covariate imbalance between treatment arms before and after adjusting for their propensity quintile. This will be done using a two-way analysis of variance model which includes main effects for propensity score quintile (codes as a class variable with 4 degrees of freedom) and treatment arm. The F-statistic for treatment arm after adjustment for propensity score quintiles will then be compared with the F-statistics for treatment arm prior to adjustment for propensity score quintile to determine whether balance was achieved after stratification based on the propensity score.

PRE-MODE

Furthermore, the propensity score will be evaluated for good calibration as measured by the propensity score predicted and observed proportions of treatment group arms within quintiles of the propensity score. To investigate whether propensity scores removed bias due to differences in covariates between studies and to compare binary study endpoints after stratification of patients by propensity scores Cochran-Mantel-Haenszel tests were performed.

Comparisons between the patients of the phase 2 study and the historical control group will be performed for LPFS, OS, motor function and ambulatory status.

10 Statistics

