10.2. Statistical analyses

10.2.1 Primary endpoint:

The primary endpoint (LPFS of MSCC) will be evaluated based on the sample size calculations described above. The evaluation will be performed in those patients, who are available for assessment of the primary endpoint and have received at least 80% of the planned RT dose. Due to the open nature of the study, a blind data review is not necessary. The safety population includes all patients who have received at least 1 fraction of high-precision RT.

LPFS is defined as freedom from progression of motor deficits during RT and freedom from an in-field recurrence of MSCC (i.e. freedom from motor deficits due to a recurrence of MSCC in the previously irradiated parts of the spine) following RT [5]. Deterioration of motor deficits during RT will be counted as LPFS of 0 months. Freedom from an in-field recurrence following RT will be referenced from the last day of RT. To investigate clinically important, sustainable effects of precision radiotherapy and avoid over-evaluation of early temporal shifts without any longer term relevance, study design and analysis focuses on binary endpoints evaluated at 6-months rather than time-to-event analyses.

10.2.2 Secondary endpoints:

Secondary endpoints:

An improvement or deterioration of the motor function will be defined as a change of at least 1 point on a 5-point scale [17]. Effect of RT on motor function and post-RT ambulatory rates will be evaluated directly after RT and at 1, 3 and 6 months following RT in those patients who are alive and available for assessment. To investigate whether propensity scores removed bias due to differences in covariates between studies and to compare binary study endpoints after stratification of patients by propensity scores Cochran-Mantel-Haenszel tests were performed. P-values of <0.05 are considered significant.

Overall survival (OS) will be counted from the last day of RT. To investigate clinically important, sustainable effects of precision radiotherapy and avoid over-evaluation of early temporal shifts without any longer term relevance, study design and analysis focuses on binary endpoints evaluated at 6-months rather than time-to-event analyses. The analysis of OS will be conducted in the intent-to-treat population.

Data regarding sensory deficits, sphincter dysfunction, pain, distress and toxicity will only be assessed in the phase 2 study.

11 Ethical and Legal Principles

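### As literally written, the secondary OS comparison requires at least 80% of planned RT dose from controls but sets no dose rule for phase 2 patients

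*Combined protocol and SAP*

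**What the plan says.** - **Control group (section 9).** Besides meeting the trial's inclusion and exclusion criteria, "patients of the historical control group must have received at least 80% of the planned RT dose". The stated reason is "to be consistent with efficacy analysis of phase II study". The rule is a condition of entry to the group, and no endpoint is excepted.
- **Endpoints compared (section 9).** Comparisons with this group "will be performed for LPFS, OS, motor function and ambulatory status".
- **Phase 2, primary endpoint (10.2.1).** LPFS is evaluated in patients "available for assessment of the primary endpoint and have received at least 80% of the planned RT dose".
- **Phase 2, safety (10.2.1).** "The safety population includes all patients who have received at least 1 fraction of high-precision RT".
- **Phase 2, OS (10.2.2).** "The analysis of OS will be conducted in the intent-to-treat population". The term appears nowhere else in the text available and is not defined. Sections 8.3.4 and 10.2.2 both count OS from the last day of RT.
- **Phase 2, motor function and ambulatory status (10.2.2).** These are evaluated "in those patients who are alive and available for assessment", with no dose rule stated at that point.
- **Source of controls (section 9).** "The patients of the control group are part of an already existing anonymized database". The document does not say whether outcomes are held for patients below 80% of dose.

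**The concern.** For LPFS the dose rule is the same in both groups. For OS, the text followed as written gives two different rules. Patients who stop RT early, including those who die during it, are removed from the control group and kept in the phase 2 group. Receipt of 80% of dose is known only after treatment starts, so this is selection of one group on a post-baseline event.

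If early stoppers survive less well, which is plausible but not quantified in the documents, the remaining controls look better than all treated controls would. The comparison then leans against 5x5 Gy. The ten propensity factors are all measured before RT, so they can balance the part of early stopping that they predict but not the rest.

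Two analysts could also build different OS sets from this text. In a non-randomised comparison that choice should be fixed before the outcomes are seen.

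**Working it through.** **Step 1. The rules side by side.**

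| Endpoint | Phase 2 dose rule | Control dose rule |
|---|---|---|
| LPFS | at least 80% (10.2.1) | at least 80% (section 9) |
| OS | none stated; intent-to-treat, undefined (10.2.2) | at least 80% (section 9) |
| Motor function, ambulatory status | none stated in 10.2.2; alive and assessable | at least 80% (section 9) |

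Both regimens have five fractions, so 80% means 0.80 × 5 = 4 fractions. Only patients who stop before the fourth fraction are affected.

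**Step 2. Who is in the phase 2 OS set.** OS time starts on the last day of RT, so an enrolled patient who receives no RT has no time origin. In practice the set is the patients who started RT, which is the safety population of 10.2.1.

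**Step 3. What the plan's own figures say.** Section 10.1 allows about 10% of enrolled patients to be ineligible for efficacy analysis: 40 × 1.10 = 44, as stated. This is not used below as the share of controls removed, because it concerns phase 2 patients and pools early loss to follow-up with discontinuation. For controls, section 9 goes from 680 to more than 600. All criteria together therefore remove fewer than 80/680 = 11.8%, and the share due to dose alone is not given.

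**Step 4. Illustration of size.** The documents give no OS rate, no share of controls removed for dose (e) and no survival among them (s). Assumptions: 50% 6-month OS in all controls, e from 2 to 10%, s from 10 to 50%, 44 versus 600 patients, no propensity adjustment.

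Control OS after removal = (0.50 − e × s)/(1 − e). For example, (0.50 − 0.10 × 0.10)/0.90 = 0.544.

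| e | s = 10% | s = 30% | s = 50% |
|---|---|---|---|
| 2% | 50.8% (+0.8 points) | 50.4% (+0.4) | 50.0% (0) |
| 5% | 52.1% (+2.1) | 51.1% (+1.1) | 50.0% (0) |
| 10% | 54.4% (+4.4) | 52.2% (+2.2) | 50.0% (0) |

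Unadjusted SE of the difference = √(0.25/44 + 0.25/600) = 0.078. The largest shift is 0.0444/0.0781 = 0.57 SE. With the roughly 400 controls of section 10.1 the SE is 0.079 and the largest shift is 0.56 SE.

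**Step 5. Direction.** With z = shift/SE and no true difference, the chance of a false finding for controls is Φ(−1.96 + z), and for 5x5 Gy Φ(−1.96 − z). At s = 10% and e = 2, 5 and 10%, the first rises from 2.5% to 3.2%, 4.5% and 8.2%. The second falls from 2.5% to 1.9%, 1.3% and 0.6%.

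**Step 6. What the propensity score can remove.** Assume 60% of controls have ECOG 1-2 with 66.7% OS, 40% have ECOG 3-4 with 25% OS (0.60 × 0.667 + 0.40 × 0.25 = 0.50), and only ECOG 3-4 patients stop early. If 12.5% of them stop, irrespective of prognosis within that level, then e = 0.40 × 0.125 = 5% and s = 25%. Crude control OS becomes (0.50 − 0.05 × 0.25)/0.95 = 51.3%, a rise of 1.3 points, but the shift within each ECOG level is zero. Bias survives adjustment only where early stopping carries prognostic information beyond the ten factors.

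**The case against.** **Intent-to-treat may be meant for both groups.** This reading is possible: it would let the OS sentence override the dose rule in section 9. It is the less literal reading, because section 9 removes under-dosed controls at entry and excepts no endpoint. The text has to settle it.

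**The propensity score deals with it.** Partly right. ECOG score, ambulatory status, visceral metastases and primary tumor plausibly explain some early stopping, and step 6 shows that this part can be removed. A reader might infer that the score can do nothing about a post-baseline selection; that is too strong. It cannot be relied on to remove all of it.

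**The illustration overstates the effect.** This largely stands. The figures are unadjusted, while the plan stratifies on the propensity score. The 10% case needs nearly all of the fewer than 80 removed controls to be dose exclusions, although section 9 pools them with every other eligibility failure. The upper corner is therefore closer to a bound than to an expected value.

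**Motor function and ambulatory status show the same mismatch.** A reader might infer this from 10.2.2, but the documents do not establish it. Section 10.1 makes patients who discontinue RT prematurely ineligible for efficacy analysis, and section 9 ties the control rule to that same general term. Section 10.1 is written around LPFS, so this is not conclusive, but motor function fits naturally under efficacy. It calls for a clarification, no more.

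**Conclusion.** The point holds for OS on the literal text: controls must have at least 80% of planned dose, while the phase 2 OS set is undefined and, in practice, is everyone who started RT. The mismatch can bias the secondary OS comparison. If early stoppers survive less well than others with the same baseline factors, the bias runs against 5x5 Gy.

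The size is unknown and may be near zero, since the course is five fractions in one week and few patients may stop before the fourth. Under the assumed inputs the unadjusted shift in control OS is 0 to 4.4 points, at most 0.57 SE.

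Two stronger inferences are not supported. A reader might think the mismatch inflates a claim of OS benefit; under the plausible direction it does the reverse. A reader might also think it undermines the primary result; it does not, because the 80% rule applies to both groups for LPFS. OS is secondary and the plan claims no power for it. This is an avoidable difference that should be corrected, held with medium confidence.

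**What to change.** In sections 9 and 10.2.2, state one OS analysis set and apply it identically to both groups.

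- **Preferred.** All patients who meet the baseline inclusion and exclusion criteria and started RT, with no dose condition and with deaths during RT counted as events. Report OS in the 80%-dose set of both groups as a sensitivity analysis.
- **Fallback, if the database lacks outcomes for controls below 80% of dose.** Use the 80%-dose set in both groups for the OS comparison, and report phase 2 intent-to-treat OS descriptively.
- **Clarification only.** State that the motor function and ambulatory comparisons use the 80%-dose set in both groups, among patients alive and available for assessment.

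Cost: a few sentences and one sensitivity analysis. The preferred set also needs control outcomes that the documents do not confirm exist, and the propensity model, strata and balance checks must be redone on the enlarged control set. The fallback and the clarification need no control data beyond those already planned. Sample size, treatment and visits do not change.

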11.1 Ethics committee vote

The study protocol will be submitted to the ethics committee responsible. The positive vote of the ethics committee has to be communicated to the coordinating investigator. (**Appendix V**)

11.2 Official registration

Because the study includes radiotherapy, an application must be submitted to the Expert Committee of the German Society for Radiation Oncology (DEGRO) and, if required by the Expert Committee, additionally to the Bundesamt für Strahlenschutz (German Federal Office for Radiation Protection).

11.4 Patient information and informed consent

Patient information and informed consent will be submitted along with the study protocol for evaluation by the ethics committee responsible. Before inclusion in the study, each patient will be fully informed about the content and procedure of the study (**Appendix I**).

If the potential study patient has received the necessary information and if the investigator is sure that the patient has understood this information, the patient will be asked to give his/her consent by signature (**Appendix II**).

The patient will receive a copy of the patient information and the signed informed consent form. The investigator must also inform the patient that he/she has the right to withdraw consent to participate in the study at any time and without having to give any reasons. Patients must be informed that the data collected as part of the study will be documented anonymously and will then be forwarded for scientific evaluation. This is also the appropriate point to indicate the patient consent to data protection.

11.5 Declaration of Helsinki

The study will be conducted in accordance with the principles laid out in the Declaration of Helsinki and in accordance with the principles of good clinical practice (GCP).

11.6 Data protection

Data will be collected in accordance with the regulations set out in the Data Protection Act. All findings from the clinical study will be stored on electronic data storage devices and treated with utmost confidentiality. Organization measures have been taken in order to prevent the data from being communicated to unauthorized persons. Patients will only be identified via their individual patient numbers throughout the entire documentation and evaluation phase and their full name will not be used.

12 Data Management

12.1 Patient identification list

All data relating to patients will be recorded in a pseudonymous way. Each patient will be identifiable only by the unique patient number. A patient identification list will only be kept in the relevant study centers and will not be forwarded to the sponsor.

12.2 Documentation forms

Data collection will be done using the case report forms (CRFs) (**separate document**).

The data documentation forms have to be filled in using a ballpoint pen. Do not use fountain pens or pencils. Corrections have to be made as follows: cross the error out once with a straight line, enter the correct information next to it and note the date and/or reason for correction. Comments have to be made if data fields cannot be filled in because of missing information.

The forms should be filled in as soon as possible and should be submitted to the principal investigator of the contributing center for review, signed, dated and forwarded to the coordinating investigator. After review and clarifying potential questions, the coordinating investigator will forward the forms to the study management office (“Zentrum für Klinische Studien” at the University of Lübeck).

12.3 Monitoring

Monitoring will be performed by the “Zentrum für Klinische Studien” at the University of Lübeck. The frequency of monitoring visits per site will be defined depending on the recruitment rate and the quality of data.

12.4 Direct access to source data / documents

The sponsor should ensure that it is specified in the protocol or other written agreement that the investigator(s)/institution(s) will permit trial-related monitoring, audits, IRB/IEC review, and regulatory inspection(s), providing direct access to source data/documents.

Appendix III Distress (quality of life) (JC Holland distress thermometer)

How much distress have you been experiencing in the past week, including today?	Please indicate to what extent you have felt distress on the thermometer and indicate the reasons for this distress below.	

Very distressed
  
Not at all distressed
	
Practical Problems
 
  Living situation  Insurance  Work/school  Transportation  Child care 	
Physical Problems
 
  Pain  Nausea  Exhaustion  Sleep  Movement/mobility
	
Family Problems
 
  Partner  Children 	
  Washing, dressing  Appearance  Breathing  Mouth sores
	
Emotional Problems
 
  Worry  Fears  Sadness  Depression  Anxiety 	
  Food/eating  Digestion  Constipation/diarrhoea  Gastrointestinal changes  Changes in urination  Fever
	
Spiritual/Religious Concerns
 
  Relating to God  Loss of faith 	
  Dry/itching skin  Dry/congested nose  Tingling in hands and feet  Feeling swollen  Sexual problems

Other Problems:
 <hr/> <hr/>		

Holland, JC. Update: NCCN practice guidelines for the management of psychosocial distress. *Oncology* 1999; 13: 459–507.

Appendix IV**Eastern Cooperative Oncology Group (ECOG) – Performance Status**

Grade	ECOG performance status
0	Fully active, able to carry on all pre-disease performance without restriction
1	Restricted in physically strenuous activity but ambulatory and able to carry out work of a light or sedentary nature, e.g., light house work, office work
2	Ambulatory and capable of all self-care but unable to carry out any work activities; up and about more than 50% of waking hours
3	Capable of only limited self-care; confined to bed or chair more than 50% of waking hours
4	Completely disabled. Cannot carry on any self-care. Totally confined to bed or chair
5	Dead

PRE-MODE

Appendix V: Ethics committee vote

PRE-MODE

Appendix VI: Insurance
